7.0 DATA COLLECTION AND MANAGEMENT

7.1 Data Collection Elements, Source, And Method Of Collection

For recruitment purposes only, a data set limited to name, email, telephone number, and Study ID number will be generated manually. For analysis, data from the assessments will include the Study ID number and demographic factors (age, gender, race, ethnicity), medications, and supplements.

7.2 Data Management

Research Data Capture System

This project will be utilizing People Science's proprietary platform, Chloe. All data is securely stored on People Science Amazon Web Services HIPAA compliant servers. The platform contains modules for building and managing forms / surveys, landing pages, marketing outreach with tracking tools for recruitment, audited electronic consent forms, data management and analytics using an integrated relational database. Data from completed assessments will automatically be collected for analysis. Study monitoring can be done using reporting features.

7.3 Data Management at Study Completion

For longer term storage of the data that will reduce risk of a data breach while still permitting that the data be verifiable (audited) the dataset will be de-identified - no names, etc., and all dates turned into time- and coded, and the key to the code will be housed in a separate location. The data will be maintained under password protection in the database.

8.0 CODING OF DATA

The dataset for recruitment (name, telephone number and Study ID number) and the data listed in Section 7.1 for analysis will be stored on a password secured database with access only to designated study team members and the study investigator.

9.0 STATISTICAL CONSIDERATIONS.

9.1 Sample Size Estimation and Justification

We anticipate screening up to 100 individuals to achieve a final sample size of approximately 50 evaluable participants. To measure our primary outcome, a single question 10-point visual analogue rating scale (VAS) will be used to reflect motivation after consumption of the Study Product, THC-Only Product, or Placebo. . The average difference in VAS responses between these 3 groups will be measured and analyzed.

Up to 20 post-product use questions, and up to 15 daily survey questions will be collected to reflect any changes in motivation, level of energy, focus, and appetite during the study period. The average difference in responses between Study Product, THC-Only Product, and Placebo will be measured and analyzed as secondary outcomes.

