1.0 OBJECTIVES AND ENDPOINTS

| Objectives | Endpoints/ Measurements |
|---|--|
| Primary Objective | |
| To observe the effect of various cannabinoid-containing products on motivation. | Change in average motivation score by 1 point as measured by a 10-point visual analogue rating scale (VAS) collected between the cannabinoid products and placebo use sessions. |
| Secondary Objective | |
| To observe the effect of cannabinoid products on energy level, focus, and appetite. | Change in average score by 1 point as measured by a 10-point visual analogue rating scale (VAS) between the cannabinoid products and placebo use sessions. |
| Exploratory Objective | |
| To observe changes in overall symptoms and quality of life. To identify improvements for future participant centered study designs using participant feedback. | Changes in overall symptoms and quality of life to be assessed based on MEFA questionnaire responses. Evaluation of study participant experiences based on the experience survey. This may include design and use of app-based data collection tools. |

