9.6 Statistical Analysis Plan

The primary objective of this study is to determine the impact of Phylos’ study product on motivation as measured by the change in VAS scores from approximately 50 participants. Univariate statistics will be generated to describe the distribution of patient characteristics and outcome data. Continuous variables will be described using means, standard deviations, minimums and maximums while categorical variables will be described using counts and percentages. VAS scores will be compared from baseline pre-product use; and at end of study (post-product use) of the same individuals. We will analyze up to 58 participants to achieve at least 90% power to detect a mean change in VAS scores of 1 point (SD=2) from baseline with a type I error of 0.05 (two-sided) assuming a paired means dependent Wilcoxon Signed-Rank test. We are testing the null hypothesis that there is no difference between pre-product use and post-product use mean VAS scores within study participants. Summary statistics will be generated, and paired differences between pre-product use and post-product use VAS scores will be reported, along with 95% confidence intervals.

Additionally, parametric linear mixed models will be employed to simultaneously account for correlated observations and adjust for confounding variables (Proc Mixed, SAS). Several covariance structures, including compound symmetry and unstructured, will be evaluated by comparing AIC and BIC to identify optimal model fit. Random slope and intercept will also be considered in a similar manner. Patient characteristics (i.e. age and sex) will be included in adjusted models a priori for confounding control. Directed acyclic graphs will be employed to select other potential confounding variables and identify biases during the model fitting process. Large differences will be further examined and may help identify where further calibration of estimation models are needed.

Stratified and interaction analyses will be employed to detect between-subgroup differences in outcomes. Specifically, we will test the difference in VAS score change between Study Product, THC-Only Product, and Placebo groups. Testing of these differences will be conducted by including 2-way product terms between the exposure and covariate of interest in linear mixed modeling. A significant interaction will be defined by an interaction coefficient with a p-value < 0.05.

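### No primary contrast or multiplicity rule is set for the three-product comparison of the primary motivation VAS; if two or three pairwise tests at 0.05 can each support the primary claim, the familywise error is about 9% or 12%

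*Combined protocol and SAP*

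**What the plan says.** Three parts of the document bear on the primary comparison.

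- **Section 1.0.** The primary objective concerns several cannabinoid products. The endpoint is a one-point change in average motivation VAS "collected between the cannabinoid products and placebo use sessions". The design has two active products, Study Product and THC-Only.
- **Section 9.1.** For the same single-question VAS, "The average difference in VAS responses between these 3 groups will be measured and analyzed". No test, significance level or success rule is attached.
- **Section 9.6.** The primary objective is the effect of the sponsor's "study product on motivation as measured by the change in VAS scores from approximately 50 participants". The error rate and power are then given for a pre/post comparison, "with a type I error of 0.05 (two-sided) assuming a paired means dependent Wilcoxon Signed-Rank test", and the null is single: "We are testing the null hypothesis that there is no difference between pre-product use and post-product use mean VAS scores within study participants". The product is not named. Later in 9.6, under the stratified and interaction analyses in the mixed model, the plan says that VAS change will be tested between the three products. The only threshold there is an unadjusted p < 0.05 for an interaction coefficient.

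No section ranks the product contrasts, requires an overall test first, or adjusts for their number.

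**The concern.** Three products give two active-versus-placebo contrasts and three pairs in all. Sections 1.0 and 9.1 place this comparison at the level of the primary outcome, and 9.6 confirms that it will be tested. With no rule on which contrast carries the primary claim, a significant result on any of them could be reported as meeting the primary objective, and the choice could be made after the data are seen. The plan would offer no protection at 5% against that.

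Choosing between a pre/post and a between-product analysis does not by itself settle this. If the primary analysis becomes two separate product-versus-placebo contrasts, a rule is still needed. If it becomes one named contrast, the problem is resolved. Section 12.5 says that results may inform participants' later product purchases, so a false product claim would have consequences.

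**Working it through.** **Inputs.** From 9.6: two-sided alpha 0.05, power of at least 90%, up to 58 participants, a mean change of 1 point and SD 2 (standardised effect 1/2 = 0.5). From 9.1: about 50 evaluable. From 6.1 and 9.3: each evaluable participant contributes data on all three products.

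**1. The plan's own figure.**
- Normal approximation: n = (SD × (z₀.₉₇₅ + z₀.₉₀)/δ)² = (2 × (1.960 + 1.282)/1)² = 42.03, so 43.
- Noncentral t: 44.
- Signed-rank test: 44/0.955 = 46.1, so 47 (efficiency under normality); 44/0.864 = 50.9, so 51 (lowest efficiency).
- Power at n = 58: 96.3% (t) and 95.5% (signed-rank, 0.955).

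The stated power of at least 90% reproduces for one test at 0.05.

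**2. Familywise error when the products do not differ.** Assume equal variances and covariances. Study Product minus placebo and THC-Only minus placebo share the placebo term, so their correlation is σ²/(2σ²) = 0.5.
- Two contrasts against placebo, each at 0.05: the chance that both are significant is 0.0093 (bivariate normal, correlation 0.5). At least one: 0.05 + 0.05 − 0.0093 = 0.0907. If independent: 1 − 0.95² = 0.0975.
- Three pairs, each at 0.05: the studentized range for three means, beyond 1.960 × √2 = 2.772, gives 0.1223. If independent: 1 − 0.95³ = 0.1426.

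Simulated three-product within-person data with paired t tests (100,000 runs at each n) agree:

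| Rule | n = 50 | n = 58 |
|---|---|---|
| One contrast | 5.1% | 5.1% |
| Either active versus placebo | 9.2% | 9.3% |
| Any of three pairs | 12.4% | 12.5% |
| Overall test first, then pairs | 5.1% | 5.0% |

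A fixed order also holds 5%: a later contrast is tested only after the one before it is significant, so when no products differ any error requires an error on the first.

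**3. Power under the possible rules (1 point, SD 2).** The first contrast in a fixed order is tested at the full 0.05. At n = 50 its power is 93.4% (t) or 92.3% (signed-rank, 0.955); at the lowest efficiency, 0.864, it is 89.4%. Bonferroni would cost more:

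| Signed-rank power, efficiency 0.955 | n = 50 | n = 58 |
|---|---|---|
| Two contrasts, alpha 0.025 | 86.9% | 91.8% |
| Three contrasts, alpha 0.0167 | 83.0% | 89.0% |

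**4. Dependence on the SD.** The documents give SD 2 for change from baseline and no SD for a difference between products. At n = 50, alpha 0.05 and a 1-point difference, the noncentrality is √50/SD. The SDs other than 2 below are illustrative assumptions.

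| Assumed SD of the between-product difference | √50/SD | Power (paired t) |
|---|---|---|
| 1.5 | 4.71 | 99.6% |
| 2 | 3.54 | 93.4% |
| 2.5 | 2.83 | 79.2% |
| 3 | 2.36 | 63.7% |

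**The case against.** A reader might infer that the false-positive rate of the primary claim is 9–12% and that the plan's 5% is wrong. The documents do not support that, for three reasons.

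- Nothing says that pairwise tests at 0.05 will be run on the primary VAS or that any one of them suffices. Section 9.1 promises only that the difference will be measured and analysed.
- The 0.05 in 9.6 is attached to one pre/post test with one null hypothesis. Comparing it with the error of a different set of tests does not show it to be wrong for its own test.
- Some readings give 5%. Section 9.6 words the objective around the study product, which may mean one contrast. The endpoint in 1.0 could mean active sessions pooled against placebo. A three-level product term could be tested overall first.

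All of this stands, and it makes the 9% and 12% conditional. It does not remove the gap. The single-contrast reading of 9.6 sits beside the plural products in 1.0 and the three groups in 9.1, and the phrase about the study product leaves its comparator open (placebo, THC-Only or baseline). An overall test first is a valid rule, but the plan does not state it.

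It is also fair to say that the more basic defect is the undefined primary contrast. Naming one contrast would cure both, and the fix does so.

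**Conclusion.** The concern holds in conditional form. The primary VAS is to be compared across three products, and no primary contrast, order, overall test or adjustment is set. If each contrast is tested at 0.05 and any one counts, the familywise error is 9.1% for the two contrasts against placebo and 12.2% for all three pairs. If one contrast is primary, or an overall test comes first, it is 5%. The current text does not decide between these.

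The error figures assume no product differences, equal variances and covariances, and complete data on all three products. The statement that the first contrast keeps about 92–93% power with 50 participants rests on carrying SD 2 over from change from baseline to the between-product difference. The documents do not state this, and the power falls quickly if the SD is larger. The plan should settle the point before analysis; it does not call for a redesign.

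**What to change.** Add one paragraph to 9.6:

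1. Study Product versus placebo on the motivation VAS is the primary contrast, tested first at two-sided 0.05.
2. Study Product versus THC-Only is tested at 0.05 only if the first is significant.
3. THC-Only versus placebo is tested at 0.05 only if the second is significant.
4. Any contrast not reached is reported descriptively with its confidence interval.

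An acceptable alternative is an overall three-product test at 0.05, with pairwise tests only if it is significant; with three products this also holds the error at 5%. Sections 1.0 and 9.1 should then name the same primary contrast as 9.6. The paragraph should also state the SD assumed for the between-product difference, since the present power statement is for change from baseline.

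The cost is wording only: no added participants, visits or data, and no alpha taken from the first contrast. The downside of the fixed order is that later contrasts cannot be claimed if an earlier one fails.

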9.2 Projected Study Timeline - Accrual, Data/Sample Collection, Completion

The total sample size for this observational study will be approximately 58 participants.

We anticipate enrollment to be complete in 4 months. Data analysis will be complete in 2 months, and a CSR and lay summary will be complete in another 1 month. Altogether, the study duration is estimated to be 7 months.

The final analysis will take place after approximately 50 evaluable participants have completed all final study assessments (i.e. product use sessions, questionnaires, surveys). These activities will be completed approximately seven weeks after enrollees initiate participation in the study.

9.3 Evaluable Participants

Participants will be considered evaluable for analysis if they complete all assessments in at least two product use sessions within each group of the study.

9.4 Covariates and Subgroups

Demographic and baseline values will be collected and analyzed on all participants. Data on age, sex, race/ethnicity, medical history including prior cannabis use, medical diagnoses, prescriptions, alcohol use, smartphone operating system (Android or iOS) will all be collected and included in univariate, bivariate, and multivariate analyses. Subgroup analyses will be

conducted to examine differences in outcome by all covariates available.

9.5 Missing Data

Missing data will be imputed with a value of “999”. The proportion of missingness will be evaluated among all covariates and outcome variables. If data are missing on a variable in under 5% of cases and the assumption of missing completely at random can reasonably be made, only observed data will be used in the analysis. If a variable is missing within a range of 5%-40% of cases, use of multiple imputation will be evaluated. Regression analyses will be conducted using only complete cases.

9.6 Statistical Analysis Plan

The primary objective of this study is to determine the impact of Phylos’ study product on motivation as measured by the change in VAS scores from approximately 50 participants. Univariate statistics will be generated to describe the distribution of patient characteristics and outcome data. Continuous variables will be described using means, standard deviations, minimums and maximums while categorical variables will be described using counts and percentages. VAS scores will be compared from baseline pre-product use; and at end of study (post-product use) of the same individuals. We will analyze up to 58 participants to achieve at least 90% power to detect a mean change in VAS scores of 1 point (SD=2) from baseline with a type I error of 0.05 (two-sided) assuming a paired means dependent Wilcoxon Signed-Rank test. We are testing the null hypothesis that there is no difference between pre-product use and post-product use mean VAS scores within study participants. Summary statistics will be generated, and paired differences between pre-product use and post-product use VAS scores will be reported, along with 95% confidence intervals.

Additionally, parametric linear mixed models will be employed to simultaneously account for correlated observations and adjust for confounding variables (Proc Mixed, SAS). Several covariance structures, including compound symmetry and unstructured, will be evaluated by comparing AIC and BIC to identify optimal model fit. Random slope and intercept will also be considered in a similar manner. Patient characteristics (i.e. age and sex) will be included in adjusted models a priori for confounding control. Directed acyclic graphs will be employed to select other potential confounding variables and identify biases during the model fitting process. Large differences will be further examined and may help identify where further calibration of estimation models are needed.

Stratified and interaction analyses will be employed to detect between-subgroup differences in outcomes. Specifically, we will test the difference in VAS score change between Study Product, THC-Only Product, and Placebo groups. Testing of these differences will be conducted by including 2-way product terms between the exposure and covariate of interest in linear mixed modeling. A significant interaction will be defined by an interaction coefficient with a p-value < 0.05.

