4.0 STUDY ACTIVITY CALENDAR

Table 4.1 Study Calendar

| Protocol Activities | Screening ^(a) | Baseline ^(b) | Study Duration | | | | | | | | |
|---|--------------------------|-------------------------|---|-----------------------|------------------------------------|---|-----------------------|------------------------------------|---|-----------------------|---|
| | | | Product Use Period 1 ^(c) (Up to 7 Days) | | | Product Use Period 2 ^(c) (Up to 7 Days) | | | Product Use Period 3 ^(c) (Up to 7 Days) | | |
| | Up to Day -14 | Up to Day 14 | Product Use Session 1 | Product Use Session 2 | Product Use Session 3 / Cross-Over | Product Use Session1 | Product Use Session 2 | Product Use Session 3 / Cross-Over | Product Use Session1 | Product Use Session 2 | Product Use Session 3 / End of Study ⁽ⁱ⁾ |
| Informed Consent | X | | | | | | | | | | |
| Medical History | X | | | | | | | | | | |
| Demographics | X | | | | | | | | | | |
| Concomitant Medications | X | | | | | | | | | | |
| Eligibility Confirmation | X | | | | | | | | | | |
| Product Delivery Receipt | | X | | | | | | | | | |
| Randomization ^d (Study Product, THC Only Product, or Placebo Group) | | X | | | | | | | | | |
| MEFA Questionnaire ^e | | X | | | X | | | X | | | X |
| Daily Product Use Survey ^f | | | X | X | X | X | X | X | X | X | X |
| Adverse Event Survey ^g | | | X | X | X | X | X | X | X | X | X |
| Cross-Over ^h (Study Product, THC Only, or Placebo Group) | | | | | X | | | X | | | |
| Experience Survey | | | | | | | | | | | X |

- a. Screening activities to occur within 14 days prior to Baseline (Day -14).
- b. Baseline activities to occur up to 14 days prior to study product use sessions (Day 14).
- c. Study duration to take place up to 21 days total across 7 days maximum within 3 periods.
- d. Participants to be randomized into the Study Product, THC-Only Product, and Placebo groups for each Product Use Period.
- e. MEFA (Motivation, Energy Level, Focus, and Appetite) Questionnaire to be administered during Baseline and at the end of Product Use 3 sessions.
- f. Daily Product Use Surveys to be administered at the end of each product use session.
- g. Any adverse event occurrence to be reported after the product use session.
- h. Participants cross-over into either Study Product, THC-Only Product, or Placebo group upon completion of Product Use Period 1 and 2.
- i. Participants to complete an experience survey at the end of the study.

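### The only powered test in 9.6 compares baseline with end of study and leaves product out, while the primary endpoint is a difference from placebo that has no named contrast, null hypothesis or power

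*Combined protocol and SAP*

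**What the plan says.** Section 1.0 sets the primary endpoint as a 1-point change in average motivation VAS, "collected between the cannabinoid products and placebo use sessions". Section 9.1 repeats the between-product aim for the primary outcome: "The average difference in VAS responses between these 3 groups will be measured and analyzed". Sections 4.0 and 6.1 describe three randomised periods (Study Product, THC-Only, Placebo), each with three product use sessions.

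Section 9.6 describes another comparison: "VAS scores will be compared from baseline pre-product use; and at end of study (post-product use) of the same individuals". Its hypothesis is explicit: "We are testing the null hypothesis that there is no difference between pre-product use and post-product use mean VAS scores within study participants". The sample size of up to 58 is justified as giving at least 90% power "to detect a mean change in VAS scores of 1 point (SD=2) from baseline", two-sided alpha 0.05, by a paired signed-rank test.

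The product comparison appears only in the last paragraph of 9.6, among the subgroup and effect-modification analyses: "Specifically, we will test the difference in VAS score change between Study Product, THC-Only Product, and Placebo groups". The method given there is: "Testing of these differences will be conducted by including 2-way product terms between the exposure and covariate of interest in linear mixed modeling". An interaction coefficient with p below 0.05 counts as significant.

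On data collection, Table 4.1 footnote f reads: "Daily Product Use Surveys to be administered at the end of each product use session". At baseline the calendar marks only the MEFA.

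**The concern.** The test that carries the power claim does not use the placebo period. It asks whether motivation differs before and after participation, and cannot separate a product effect from expectation, placebo response or drift over time. Two errors are possible.

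- **False credit.** A response shared by all three products makes the test significant, and the result could be attributed to the Study Product.
- **Dilution.** If end of study means Period 3 Session 3, the test pools participants who finish on different products, so a real Study Product effect is averaged with whatever the other two do.

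The comparison that does answer the objective is left open. Study Product against Placebo, THC-Only against Placebo, the two actives pooled against Placebo, and a three-way test would all fit the text. Interaction terms between exposure and a covariate test effect modification, not a product main effect, unless the covariate is meant to be time; 9.6 does not say. Without a named contrast, the choice among pre/post, pooled and pairwise results can be made after the data are seen.

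The pre-product score also has no clear source. The daily survey follows product sessions only, and the documents do not say whether the baseline MEFA contains the motivation VAS item.

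**Working it through.** **Inputs from the documents.** Effect 1 point; SD 2 for change from baseline; two-sided alpha 0.05; power at least 90%; up to 58 analysed (9.6); about 50 evaluable (9.1, 9.2). Not stated: the SD of a within-person product difference, the allocation ratio and the sequences. These are assumed below.

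**1. The plan's own figure.** Normal approximation: n = ((1.960 + 1.282) × 2 / 1)² = 42.03, so 43. The exact paired t-test needs 44. Dividing by the signed-rank test's efficiency under normality, 3/π = 0.955, gives 44 / 0.955 = 46.1, so 47. Signed-rank power is 92% at n=50 and 95.5% at n=58. The stated 90% is therefore right for the pre/post test.

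**2. Shared response, no product difference.** Every product, placebo included, shifts VAS by the same amount; SD 2; signed-rank test; 40,000 simulated trials per cell.

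| Shared shift | Rejects, n=50 | Rejects, n=58 |
|---|---|---|
| 0 | 5% | 5% |
| 0.25 | 13% | 15% |
| 0.5 | 40% | 45% |
| 1 | 92% | 96% |

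**3. Dilution, on one reading.** Assume end of study is Period 3 Session 3, a third of participants end on each product, there is no shared shift, and SD is 2. The Study Product truly adds 1 point, THC-Only adds x and Placebo 0, so the mean change is (1 + x + 0)/3.

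| x | Mean change | Power, n=50 | Power, n=58 |
|---|---|---|---|
| 0 | 0.33 | 19% | 23% |
| 0.5 | 0.50 | 39% | 45% |
| 1 | 0.67 | 62% | 68% |

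These vary by about a point with simulation error and with how the sample divides into thirds.

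**4. Power for the contrast the endpoint implies.** Paired Study Product minus Placebo, 1-point difference, noncentral t with effective n = 0.955n and noncentrality (1/SD) × √(0.955n).

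| SD of paired difference (assumed) | n=50 | n=58 | n for 90% |
|---|---|---|---|
| 1.5 | 99.5% | 99.8% | 27 |
| 2 | 92% | 95.5% | 47 |
| 2.5 | 77% | 83% | 71 |
| 3 | 62% | 68% | 102 |

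Solving for 90% power gives a largest allowable SD of 2.09 at n=50 and 2.25 at n=58.

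**5. Multiplicity.** With three independent, equal-variance normal product scores per person, n=50, no true difference and each contrast tested at 0.05, the chance of at least one false positive is about 9% for the two contrasts against Placebo and 12% for all three pairwise contrasts.

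**The case against.** The strongest reply is that the plan does commit to comparing the three products, in both 9.1 and 9.6. Section 1.0 supplies a 1-point target for the comparison with placebo, and 9.6 supplies a p < 0.05 threshold. A shared response would then show up in the planned output and need not mislead anyone. That is fair as far as it goes. But the target is not tied to an SD, alpha or sample size, the threshold is for interaction coefficients, and nothing says that the product comparison outranks the powered pre/post test.

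Second, post-product use may mean the end of each product's own period. That is a plausible reading, and under it the dilution in step 3 disappears. Step 2 does not.

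Third, the SDs in step 4 are assumed, and the endpoint averages up to three sessions. If the SD of 2 were entirely session noise in a single-score change, the difference of two three-session means would have SD 2/√3 = 1.15, with power near 100%. Strong person-by-product variation would push the other way. So the sample size is unjustified for this endpoint; it is not shown to be too small.

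Fourth, 1.0 speaks of cannabinoid products in the plural while 9.6 states the objective for the study product, so the primary contrast is not fully settled by the text. This stands: the two sections need aligning.

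Finally, given its name, the MEFA probably includes a motivation item. The documents do not confirm it.

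**Conclusion.** The concern holds. The only test with a stated null hypothesis, effect size, alpha and power answers a different question from the primary endpoint, and the product comparison lacks a named contrast, a formal null, an SD, power and a multiplicity rule.

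The mismatch follows from the text and needs no assumption. Its size does. The 13% to 92% rejection rates at n=50 assume shared shifts of 0.25 to 1 point with SD 2. The 19% to 68% dilution figures also need the Period 3 Session 3 reading, equal thirds and no shared shift, and are illustrations of that reading only. The 90% power claim transfers to the paired contrast only below the SD limits of 2.09 and 2.25, which the documents neither confirm nor exclude. This should be corrected before analysis.

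**What to change.** In 9.6:

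- Make the primary analysis the within-participant difference from Placebo in mean post-session motivation VAS, with Study Product minus Placebo as the named primary contrast, since 9.6 states the objective for the study product. Align 1.0 with it.
- State the null hypothesis for that contrast.
- Estimate it as the product main effect in a mixed model with period and sequence terms (the sequences must first be defined), with a signed-rank test on the same paired difference as sensitivity analysis.
- State how type I error is controlled if THC-Only minus Placebo or Study Product minus THC-Only is also confirmatory. Method and order are the sponsor's choice.
- Attach the power statement to the primary contrast, with a justified SD and a range such as step 4. If the SD exceeds 2, restating the power avoids enlarging the sample.
- Keep the baseline-to-end change as descriptive, and say which instrument supplies the baseline score.
- Keep exposure-by-covariate terms for subgroup questions only.

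The cost is wording. The post-session data are already scheduled, so no visits are added, and no participants are added if power is restated. The downsides are that the stated power may be less favourable (77% at n=50 if the SD is 2.5) and that the pre/post result can no longer be presented as primary.

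### The powered test in 9.6 compares baseline with end of study: its pre-product VAS has no identified source, and it does not address the section 1.0 product-versus-placebo endpoint

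*Combined protocol and SAP*

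**What the plan says.** **The test.** Section 9.6 gives the main comparison as "VAS scores will be compared from baseline pre-product use; and at end of study (post-product use) of the same individuals". Its null hypothesis is no pre-to-post difference within participants. The power statement is for the same quantity: "at least 90% power to detect a mean change in VAS scores of 1 point (SD=2) from baseline". The planned procedure is a Wilcoxon signed-rank test on the paired scores, two-sided at the 0.05 level.

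**The endpoint.** Section 1.0 defines the primary endpoint as a 1-point difference in average motivation VAS between cannabinoid-product sessions and placebo sessions. Section 9.1 says that "a single question 10-point visual analogue rating scale (VAS) will be used to reflect motivation after consumption", and that the difference among the three groups will be analysed.

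**The schedule.** Table 4.1 has no row that names the VAS. It has two outcome instruments:
- Daily Product Use Survey. Footnote f reads "Daily Product Use Surveys to be administered at the end of each product use session". The Baseline cell is empty.
- MEFA Questionnaire, given at Baseline and after the third session of each period. Section 1.0 uses it for the exploratory objective. Its items and response format are not described.

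**The numbers.** Section 9.6 says "We will analyze up to 58 participants", and section 9.1 expects "a final sample size of approximately 50 evaluable participants".

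**The concern.** There are two separate problems.

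The first is the data source. The only test with a stated null and power needs a motivation VAS taken before any product, and the protocol does not say which assessment supplies it. An analyst would have to choose the pre value after the data are in. If a MEFA item that is not the identical VAS were subtracted from a session VAS, a difference between instruments would be read as a product effect.

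The second would remain if the first were settled. In a three-period crossover, the last score belongs to the product taken last. A change from baseline to that score combines study product, THC-only product and placebo, and includes any drift or expectation effect common to all three. A positive result would not show that the study product differs from placebo, which is the comparison section 1.0 sets out to make.

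**Working it through.** **1. The plan's own power figure.** Inputs from 9.6: mean change 1, SD 2 (read as the SD of the paired change), two-sided alpha 0.05, power 90%.

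- Normal approximation: n = (SD × (z₀.₉₇₅ + z₀.₉₀) / Δ)² = (2 × (1.960 + 1.282) / 1)² ≈ 42.03, so 43. The paired t-test needs 44.
- Signed-rank test: use the paired t-test with effective n = n × 3/π (its efficiency for normal data), noncentrality = (Δ/SD) × √(effective n).
 - n = 50: effective n = 47.7, noncentrality = 0.5 × √47.7 = 3.46, power 92.3%.
 - n = 58: effective n = 55.4, noncentrality = 0.5 × √55.4 = 3.72, power 95.5%.
- A simulation with 20,000 replicates gave 92.3% and 95.5%. The smallest n reaching 90% by this formula is 47.

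The stated power reproduces. The arithmetic is sound; the question is what it is attached to.

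**2. Where the pre and post values could come from.**

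| Location of the motivation VAS | Pre-product value | End-of-study value |
|---|---|---|
| Daily survey only | none scheduled | yes |
| MEFA only | yes, at Baseline | yes, but not secured by the evaluability rule |
| Both | yes, if the item is identical | yes |

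The second row follows from section 9.3, which counts a participant as evaluable after all assessments in two sessions per group. MEFA falls only at Baseline and at third sessions. Someone who completes the first two sessions of every period is therefore evaluable without any post-product MEFA. The rule fits a VAS held in the daily survey better, but no section settles the matter.

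**3. What the baseline-to-end test estimates.** Let c be the mean change from baseline common to all products, placebo included. Let s and t be the effects of study product and THC-only product over placebo. Ignoring period and carry-over effects, the expected change is c + p_S·s + p_T·t, where p_S and p_T are the shares of participants taking each product in Period 3. The documents give no sequences or allocation ratio. Taking equal thirds as an assumption, this is c + (s + t)/3.

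- s = 1, t = 0, c = 0: the expected change is 1/3 point, although the study product beats placebo by the full target.
- s = 0, t = 0, c = 1: the expected change is 1 point, the size the test is powered to detect, although no product differs from placebo.

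The section 1.0 endpoint concerns s and t, not this mixture.

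**4. Power for study product minus placebo, difference of 1 point, signed-rank, alpha 0.05.** If SD 2 is the SD of the within-participant difference, step 1 carries over: 92.3% at 50 and 95.5% at 58. If SD 2 is the SD of a single score per product, the SD of the difference is 2 × √(2(1 − ρ)), where ρ is the correlation between a participant's two scores. The documents give no ρ, so the values below are assumptions.

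| ρ | SD of difference | Power, n = 50 | Power, n = 58 |
|---|---|---|---|
| 0 | 2.83 | 66.7% | 73.4% |
| 0.25 | 2.45 | 78.9% | 84.7% |
| 0.5 | 2.00 | 92.3% | 95.5% |
| 0.75 | 1.41 | 99.8% | 99.9% |

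The table allows nothing for averaging over sessions. If SD 2 describes one session's rating, averaging two or three would raise power by an amount the documents do not let one compute.

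**The case against.** The strongest reply is that MEFA may contain the VAS item. Its schedule matches the two time points in 9.6, Baseline and end of study. It covers the same four domains that section 1.0 scores by VAS, and section 9.4 says baseline values will be collected on all participants. Table 4.1 does not name the VAS after product use either, so its silence before product use proves little. This stands. A reader might infer that the 9.6 test cannot be run, or that no pre-product observation is scheduled. The documents do not support that, because the questionnaire's content is not in them. What remains is that the source is not identified, and that sections 1.0, 9.1 and 9.3 point away from MEFA as the carrier of the primary VAS.

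A second reply is that 9.6 also plans linear mixed models and a comparison of VAS change among the three groups. That is so, and a product comparison is not absent from the plan. But it appears under stratified and interaction analyses, is worded as a difference in change, and has no primary null or power of its own.

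A reader might also infer that a baseline VAS is needed to sharpen the product contrast. A single Baseline score is the same under both products and cancels in a within-participant difference. Scores taken before each period might help, but the documents give no correlation from which to size the gain.

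**Conclusion.** The point holds in two parts. The pre-product motivation VAS that 9.6 requires has no identified source, which is an ambiguity rather than proof that the data will be missing. The firmer defect does not depend on how that is resolved: the powered test does not estimate the primary endpoint, because its end-of-study score reflects whichever product came third.

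The endpoint itself can be estimated from the post-session scores already planned. Whether 50 to 58 participants suffice for it depends on what SD 2 describes. Read as the SD of the within-participant difference, the design keeps at least 90% power under the normal-data approximation. Read as the SD of a single score, it falls short at 50 participants for the lower correlations considered (66.7% at 0, 78.9% at 0.25) and reaches 92.3% at 0.5.

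**What to change.** 1. In 9.6, replace the baseline-to-end-of-study test and its null with the within-participant difference in mean post-session motivation VAS, study product minus placebo. State the role of the THC-only comparison, since section 1.0 speaks of cannabinoid products in the plural. If both products against placebo were primary at alpha 0.025 each, with SD 2 for each difference, power would be 86.9% at 50 and 91.8% at 58.
2. Restate the power for that contrast. Say whether SD 2 is the SD of the difference or of a single score and, if the latter, give the assumed correlation and the range of power.
3. State which instrument carries the motivation VAS. If a pre-product comparison is kept as secondary, name the scheduled assessment that holds the identical item, or add that item before product use in Table 4.1.

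Items 1 and 2 cost a rewritten paragraph in 9.6, with no extra data collection. Whether the sample size needs revisiting depends on the SD and correlation declared in item 2. Item 3 costs one sentence or, if the item has to be added, a calendar entry and a short app prompt. It should be settled before enrolment, because a missed pre-product score cannot be recovered later.
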